In addition to telephonic methods, we will attend community events (fairs, events at local malls and businesses) and also use email blasts, ResearchMatch newspaper articles and distribute flyers to recruit participants. We will recruit from the Montefiore Medical Group in Co-op City (Bartow) for participants who live, work, visit (for shopping, doctor's appointments) attend school in Co-op City or neighboring communities and will also use electronic medical records from the Montefiore Medical Group in these communities to create recruitment lists that we will use to contact participants. Our recruiter will describe study to participants in waiting area and provide contact information about the study or sign up interested participants. Flyers will be provided. Physicians in the practice may also provide flyers about study to participants and refer them to study recruitment phone line or email address.

Once it has been determined that an individual is eligible to participate and he/she agrees, an appointment is made for two screening visits. At these visits, participants perform run-in such as using the smartphone for assessing cognition and mood and also learn to track foods using the smartphone. They are also given home assignments to assess ability to perform the study tasks. Randomization occurs after screening visit #2 when participants return to the clinic with the smartphones and are judged to be eligible to proceed to study activities.

The tasks at each visit are outlined below:

5 **STUDY INTERVENTIONS**

5.1 **Interventions, Administration, and Duration**

If assigned to the Multicultural Healthy Diet, participants will:

- follow an anti-inflammatory healthy dietary pattern over the 27 month duration of the study
- attend four 1-2 hour groups sessions on shopping & cooking healthy diet in the first 2 months at Co-op City or other convenient location (up to 8hr)
- write down foods eaten 3 times/month for 18 months (18 hr)
- receive 16 monthly 20 minute phone calls and/or online program materials from coaches on following diet after the group sessions end; for participants who are difficult to reach, up to three sessions can be completed in one phone call (5 hr, 20 minutes)

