6.1. Schedule of Evaluations

Assessment	Screening: Phone Assessment	Baseline, Enrollment, R andomiza-tion: Visit 1a (Run- in Visit)	Visit 1b (Baseline)	Visit 2 (W1)	Visit 3 (W2)	Follow-up: Final Visit (W3)
Informed Consent Form	X (oral)	X (written)				
Demographics	X	X		X	X	X
Medical History			X	X	X	X
Cognitive Examination			X	X	X	X
Ambulatory Assessments	X	X	X	X	X	X
Questionnaires		X	X	X	X	
Supplement Use		X	X	X	X	X
Current Medications			X	X	X	X
Blood Chemistries, spot urine			X	X		
Vital Signs & anthropometry: Blood pressure, height, weight, body composition, eye test,			X	X	X	X
Waist/hip circumference						
Inclusion/Exclusion Criteria	X	X				
Enrollment/Randomization			X			
Intervention/Comparison Meetings and Phone Calls			X	X	X	
Adverse Events				X	X	X

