6.2.3 Follow-up visits

Clinic Visit #1 (Scheduled for eligible participants after Screening Visit #2, 2 hr)

At this visit, participants will:

- undergo cognitive testing at the clinic
- respond to questionnaires about medical history, moods & daily experiences
- receive randomization assignment to Usual Diet or Multicultural Healthy Diet
- schedule a 30 minute visit for eye test and body measurements: blood pressure, blood draw, spot urine collection, height, weight, waist/hip circumference, body composition.

At home after Visit #1 (1 hour per day for 7 days)

Participants are asked to do the following over the next seven days:

- enter food intake using the smartphone
- complete a brief survey when waking up in the morning and before going to bed
- play brief brain games four times during the day
- at the end of the 7 days, return the smartphone to the clinic after completing the exercises

Randomization

Randomization occurs after Clinic Visit #1 (Baseline) when body measurements are complete. When adequate numbers of participants (about 8-10) are randomized to start a comparison or intervention group, participants will be invited to the sessions. In the meantime they will receive informational materials about the study in preparation for the sessions.

Clinic Visit #2 (Scheduled 9 months after Visit #1, 2 hr)

This visit is identical to Visit #1.

At home after Visit #2 (1 hour per day for 7 days)

These activities are identical to at-home activities after Visit #1.

Clinic Visit #3 (Scheduled 9 months after Visit #2, 2 hr)

This visit is identical to Visit #1, except that there will be no blood tests or urine collection scheduled after the visit.

At home after Visit #3 (1 hour per day for 7 days)

These activities are identical to at-home activities after Visit #1.

Clinic Visit #4 (Scheduled 9 months after Visit #3, 2 hr)

This visit is identical to Visit #1, except that there will be no blood tests or urine collection scheduled after the visit.

At home after Visit #4 (1 hour per day for 7 days)

These activities are identical to at-home activities after Visit #1.

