7.2 Methods and Timing for Assessing, Recording, and Analyzing Safety Parameters

The MHD for healthy participants- the target of this study- is generally safe. Should participants develop health problems during the study that precludes staying on this diet (e.g. unintentional weight loss, eating disorders), the participants are advised to contact primary physician and decide the merits of continuing in the study and are free to discontinue participation. Participants are asked to report any such developments.

7.3 Adverse Events and Serious Adverse Events.

An adverse event (AE) is generally defined as any unfavorable and unintended diagnosis, symptom, sign (including an abnormal laboratory finding), syndrome or disease which either occurs during the study, having been absent at baseline, or if present at baseline, appears to worsen. Adverse events are recorded regardless of their relationship to the study intervention.

A serious adverse event (SAE) is generally defined as any untoward medical occurrence that results in death, is life threatening, requires inpatient hospitalization or prolongation of existing hospitalization, results in persistent or significant disability/incapacity, or is a congenital anomaly.

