8 INTERVENTION DISCONTINUATION

If participants have unintentional weight loss defined as 10% weight change, if BMI ≥ 25 and 5% weight change if BMI < 25 in past six months to one year or develop health issues that preclude participation in the study, the participant may be asked to withdraw or he/she may voluntarily withdraw from the study. Participants may withdraw voluntarily from participation in the study at any time and for any reason. Alternatively if the withdrawal is temporary (due to surgery or other health or other matter), they can be followed for study outcomes if practical and can rejoin study when ready. Each situation will be decided on a case by case basis.

We have considered an attrition rate of 15% from visit #1 to visit #2 and 5% thereafter between visits. However we may consider replacement of participants if the numbers projected for

attrition are higher –time permitting. If there is not enough follow-up time, then replacement will not be possible.

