For any identified important effects of the diet on cognition, we will explore which of the dietary components were mediating that effect. In particular, for the dietary components that seem to be the most different between arms at Burst 2, we will explore whether the Burst 2 measure (or the change from baseline at Burst 2) are associated with a change in the cognitive outcomes at Burst 2 using models similar to that for the primary analysis of the intervention effect. Supportive analyses may also consider formal mediation analyses or the approaches discussed in Freedman et al. 2010 (i.e., both principal components and Howe's method) as ways to efficiently combine the biomarker and self-reported measures of intake in an analysis of their association with cognitive measures. Exploratory dietary effects also include the treatment effect on HbA1c and self-reported vitamin D and choline. The treatment effect on the inflammatory markers IL6 and CRP will also be considered.

For any significant differences by treatment arm, we will examine whether there was evidence of a differential intervention effect across APOE4 groups. Exploratory analyses that examine

potentially differences in identified intervention effects by gender, race, ethnicity and age, will also be considered.

Exploratory analysis will also examine whether there was weight loss at Burst 2 relative to Burst 1 in a complete case analysis:

$$W_{i2} = \beta_0 + \beta_1 W_{i1} + \beta_2 \text{Arm}_i + \beta_3^T \text{Strat}_i + e_i.$$

and if significant changes in weight are identified, analyses will be considered to identify whether any identified intervention effects were potentially mediated by weight loss.

Handling of Missing Data

Analyses of the primary outcome will be done on an intent-to-treat basis; we will assume the data are missing at random (MAR) and use multiple imputation to impute missing measures. Rubin's rules will be used to calculate the variance of the model parameters for each analysis of interest. For secondary outcomes, approaches to address missing data will also assume MAR and approaches to address missing data will generally employ complete case adjustment methods (Little et al., 2022). For missingness rates >10%, sensitivity analyses may be performed using varying assumptions regarding the missing data model to examine whether study conclusions are robust to these differing assumptions. Further details are provided below.

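### The only planned between-arm weight analysis is a month-9 complete-case comparison of means, so later weights, individual threshold crossings and withdrawals for weight loss have no planned comparison

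*SAP*

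**What the plan says.** Protocol Section 7.2 gives weight loss as one of two examples of problems that could rule out the diet: "Should participants develop health problems during the study that precludes staying on this diet (e.g. unintentional weight loss, eating disorders". Section 8 attaches numbers: "If participants have unintentional weight loss defined as 10% weight change, if BMI ≥ 25 and 5% weight change if BMI < 25", with a look-back window of six months to one year. It says of a participant in that position that "the participant may be asked to withdraw or he/she may voluntarily withdraw from the study".

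The Schedule of Evaluations (Section 6.1) marks the row "Vital Signs & anthropometry: Blood pressure, height, weight, body composition, eye test" at baseline and at Visits 2, 3 and 4, that is, at months 9, 18 and 27. Section 6.2.3 says of Visits 3 and 4: "This visit is identical to Visit #1, except that there will be no blood tests or urine collection scheduled after the visit". Body measurements therefore stay. Coaching runs to month 18, and under Section 5.1 diet-arm participants are to "follow an anti-inflammatory healthy dietary pattern over the 27 month duration of the study".

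In the SAP, weight appears as an outcome only under Exploratory Analyses: "Exploratory analysis will also examine whether there was weight loss at Burst 2 relative to Burst 1 in a complete case analysis". The model is an ANCOVA of Burst 2 weight on Burst 1 weight, arm and the stratification factors. Its stated use is that "if significant changes in weight are identified, analyses will be considered to identify whether any identified intervention effects were potentially mediated by weight loss".

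**The concern.** The protocol defines this harm for an individual, over a stated interval, and links it to leaving the study. The planned analysis differs on all three counts.

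- **Time.** It stops at month 9, although weight is scheduled twice more and the diet continues.
- **Quantity.** It compares means, although the harm is a person passing a percentage that depends on BMI.
- **Missing data.** It uses complete cases, although the harm can itself be the reason for having no month-9 weight.

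A trial report that follows the SAP could state that mean weight did not differ at month 9 and say nothing, by arm, about people who lost substantial weight later or left because of it. The same result decides whether mediation by weight is looked at, so a diluted difference could also close that question.

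**Working it through.** **No stated figure to reproduce.** The documents give no SD, event rate or power for weight. The first two steps use the documents' own numbers. The last three are illustrations on assumed values.

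**1. Follow-up left unused.** The analysis ends at month 9.
- Diet follow-up: 27 − 9 = 18 of 27 months (67%).
- Active intervention: 18 − 9 = 9 of 18 months (50%).

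**2. Participants outside the complete-case model.** Protocol Section 3 reports 290 randomized and 260 at Visit 2.
- 290 − 260 = 30, and 30/290 = 10.3%.
- This is a floor, because Section 3 also reports a four-month pause in anthropometry during the pandemic.
- If 5 of the missing in one arm of 145 had crossed the threshold, 5/145 = 3.4% of that arm would go uncounted. If 10 had, 10/145 = 6.9%.

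**3. What a mean shows about a threshold harm.** Assume a mean weight of 80 kg, SD of change *s* of 4 to 6 kg, 130 weighed per arm (260/2) and two-sided 5%. If a fraction *f* of the diet arm loses 10% of body weight (8 kg each):
- Shift in the arm mean = *f* × 8 kg.
- SE = *s* × √(2/130), which is 0.496 kg at *s* = 4 and 0.744 kg at *s* = 6.
- Power ≈ Φ(shift/SE − 1.96).

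| *f* | Shift | Power, *s* = 4 | Power, *s* = 6 |
|---|---|---|---|
| 5% | 0.4 kg | Φ(0.81 − 1.96) = 12% | Φ(0.54 − 1.96) = 8% |
| 10% | 0.8 kg | Φ(1.61 − 1.96) = 36% | Φ(1.08 − 1.96) = 19% |

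For comparison, the shift detectable with 80% power is (1.96 + 0.84) × SE, or 1.4 to 2.1 kg.

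**4. Worst case for withdrawal.** If every affected participant left before Burst 2 without being weighed, the expected complete-case difference would be 0.0 kg and the test would reject at its nominal 5%. Set this against the attrition in step 2. With an even split (assumed), 15 of the 30 missing are in the diet arm. The 5% scenario is 0.05 × 145 = 7.25 people, 48% of those 15. The 10% scenario is 14.5 people, 97% of them.

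**5. Would a threshold count do better?** Fisher exact, two-sided, 145 per arm:

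| Diet v comparison | p |
|---|---|
| 7 v 0 | 0.015 |
| 8 v 1 | 0.036 |
| 9 v 2 | 0.060 |
| 12 v 5 | 0.13 |

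The excess is seven in every row, and the evidence weakens as background events rise. Power for a difference in proportions (normal approximation, 145 per arm) is 54% for 2% v 7%, 37% for 5% v 10%, 92% for 2% v 12% and 81% for 5% v 15%. A count shows the harm directly but is imprecise for small excesses, so it should be descriptive with an interval.

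**The case against.** **The SAP model is a step towards mediation, not the safety analysis.** This stands. Month-9 weight is the right measure for mediation of a month-9 endpoint, and the SAP leaves safety monitoring to the study team and the DSMB. A reader might infer that this ANCOVA is the trial's test of whether the diet is safe or eucaloric; neither document says so. It is still the only arm comparison of weight that is planned.

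**Weight loss could be compared elsewhere.** A reader might infer that it is never compared between arms. The documents do not support that: Protocol Section 9.3 lets a statistician review events by group when safety concerns arise, and weight loss recorded as an adverse event could be included. That review is conditional, does not mention weight or the Section 8 thresholds, and is not an analysis for reporting.

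**The 0.0 kg result is extreme.** This also stands. Withdrawal under Section 8 is only possible, and temporary leavers may be followed. No weight is scheduled between baseline and month 9, so many crossings would first be seen at Visit 2, where the weight is recorded. A reader might infer that the plan will hide a weight effect; step 4 shows how much of the attrition that would need.

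**Sensitivity analyses are allowed above 10% missingness.** They are optional, and that part of the SAP concerns primary and secondary outcomes. The imputation model covers only the ambulatory cognitive scores.

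**Conclusion.** The point holds as a gap in planned analysis. Unintentional weight loss is a harm the protocol names, and the only one it gives numeric thresholds. The single planned arm comparison of weight is exploratory, at month 9, on means, in complete cases. Two thirds of diet follow-up, all individual threshold crossings, and any withdrawal for weight loss before a month-9 weight fall outside it.

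What rests on the documents is the list of omissions, the 18 of 27 months and the 10.3% floor on missing month-9 weights. The kilogram shifts, power values and event counts are illustrations on assumed SDs and rates, and the complete-case difference of 0.0 kg is a worst case. The copy read lacks some protocol text between Sections 7.5 and 8, so the claim is limited to the SAP and the protocol text available. It is a modest issue, worth correcting because the data are already scheduled and the correction is cheap.

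**What to change.** Amend the SAP only. No visit, clinical threshold or withdrawal rule changes.

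1. **Model.** Extend the weight analysis to a mixed model of weight at months 9, 18 and 27 on baseline weight, arm, visit, arm-by-visit and the stratification factors. Report the arm difference at each visit, and keep month 9 for the mediation question. With baseline as a covariate, this model still omits anyone with no later weight, so the table below is needed as well.

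2. **Descriptive table by arm, in all randomized participants.**
   - Count those whose loss between consecutive scheduled visits reaches the Section 8 percentage for their BMI at the start of that interval. Visits are nine months apart, inside the Section 8 window; loss from baseline to month 18 or 27 would not be. Section 8 does not say which BMI applies, so state this choice as an analysis convention.
   - Label the row as weight loss regardless of intent.
   - In separate rows, give withdrawals with weight loss as the recorded reason, and participants with no post-baseline weight.
   - Give risk differences with exact 95% confidence intervals.

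**Cost.** SAP wording, one model and one table. State the limits with the results: counts may be low and intervals wide, visit weights cannot show that loss was unintentional, and withdrawal reasons may be ascertained unequally, since Protocol Section 7 asks for reports of developments tied to consuming the study diet.

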Data will be saved locally on each smartphone’s internal storage for the duration of the data collection periods and retrieved via direct connection to a workstation over USB to a central secure server after phone is returned following each assessment. Participants will complete “wake-up” surveys upon waking up in the morning. Wake-up surveys consists of a brief assessment of the previous night’s sleep (when they went to bed, when they woke up, sleep disruptions and sleep quality) and a reminder to note what they are eating by entering foods into the ASA24 as they consume them or all at once by the following morning for all foods eaten the previous day. Bedtime surveys will be completed immediately prior to going to bed, and will query individuals about the stress, physical symptoms and the fatigue they experience throughout the day. Participants will be alerted to complete the signal contingent surveys via beeps. The four signal contingent surveys will be administered randomly throughout the day and consist of questions regarding the participant’s current location, mood, stress, activity level, who they are with, and the distractibility of their environment. Immediately following the Wake-up and signaled brief surveys, participants will complete five brief cognitive tasks (described below). Each wake-up, signal contingent and bedtime survey will also query whether the individual had any liquids and what he/she drank. Three additional 7-day measurement bursts will be completed at 9, 18 and 27 months post-baseline, resulting in up to 140 assessments across the follow-up period (35 assessments on each of 4 bursts). This intensive measurement approach will allow us to explicitly examine lead-lag relationships between “cognitive health friendly” eating patterns and especially role of eating patterns that have an adverse impact on cognitive function. The burst design will permit modeling of the temporal relationship between diet and cognitive function across days, months & years. Knowledge of the time sequence is important as it will allow us to determine how long the effects of a healthy food/nutrient lasts (e.g. blueberries or folate), what dose is effective and how it is affected by subsequent ingestion of a less healthy food (French fries). The 27 month assessment period will provide three time points to assess cognitive status to establish trajectory.

[figure not shown]

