At least 50% (18 out of 35) of the scheduled sessions must be completed for each task in order for a given measurement burst to be considered valid. These 35 scores may take longer than 7 days to accumulate but must be taken without 2-week or larger gap between sessions to be included in the analysis. Each burst has a recorded burst start date; sessions recorded prior to this start date are considered part of the pre-burst training and will be discarded. The first day of the Burst 2 measurement should be inside the visit window (i.e., at least one session no earlier than 3 months and no later than 6 months than the 9-month randomization anniversary) for the Burst 2 measurement to be valid and included in the primary analysis. The domain Z-score is computed using the mean and SD for an individual session, estimated from the baseline (Burst 1) distribution and the measurement burst for an individual i at Burst j is the average task scores across the multiple sessions (up to 35) within that burst. The domain Z-score with fewer than 18 valid sessions will be treated as missing and multiply imputed for the primary analysis, which will be an intent-to-treat analysis. The details are as follows.

The mean and SD are calculated for each domain separately from the baseline measurement (Burst 1). For a given domain, let Y_{i1j}^d be the Burst 1 outcome score from domain d , $d=1,2,3$;

person i , $i=1, \dots, n$; and session $k=1, \dots, m_{i1}$, where m_{i1} is the number of successfully completed sessions at baseline for person i (which may vary by domain d), then:

$$\mu^d = \sum_i \bar{Y}_{i1}^d / n; \bar{Y}_{i1}^d = \sum_j (Y_{i1k}^d) / m_{i1}; SD^d = \sqrt{(\sum_i (\bar{Y}_{i1}^d - \bar{Y}_{1.})^2 / (n-1))}.$$

Then for a given measurement burst $j=1, 2, 3, 4$: where $j=1$ represents baseline and $j=2-4$ represents months 9, 18, and 27, respectively; the domain Z-score for subject i and Burst j is denoted by Z_{ij}^d is calculated from Y_{ijk}^d as:

$$Z_{ij}^d = (Y_{ijk}^d - \mu^d) / SD^d.$$

The three primary tasks (variable names) are:

- Z^1 =Symbol search (SYMBOL_SEARCH.median.RT.accurate_trials)
- Z^2 = Grid Memory (DOT_MEMORY.sum.error.distance.overall)
- o Z^3 = Color Shapes (COLOR_SHAPES.CorRec.rate)

The global assessment score for person i at Burst j is calculated as the average of the three domain average Z score, with Z^1 and Z^2 multiplied by negative 1 so increase is improvement:

$$Z_{ij} = (-Z_{ij}^1 - Z_{ij}^2 + Z_{ij}^3) / 3.$$

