Imputation Models for the Ambulatory Cognitive Scores

For the primary analysis, we will use the multiple imputation chained equation approach (MICE) to impute the necessary missing data to allow an ITT analysis (Azur et al. 2011). Burst measures that had fewer than 18 valid sessions for a given domain average (i.e. for \bar{Y}_{ij}^d for $d=1,2,3$; $j=1,2$) or a Burst 2 measure that started outside the Burst 2 window will be treated as missing and imputed.

A sequence of chained equations for MICE will be considered using: all variables in the primary analysis model (i.e., Arm, gender (0=female, 1=male), age at Burst 1, years of education, Burst 1 composite Z-score, and Burst 2 composite Z-score), run-in average variables for each of the tasks 1-3 in the composite outcome (\bar{Y}_{i0}^d), (averaging first 10 or fewer for each), MOCA score, indicator for in-person vs telephone MOCA, and interaction between these two MOCA variables, domain-specific Zscores based on the average of the available data from up to the first 10 sessions at Burst 1 for each of the three tasks 1-3 in the composite outcome, and the Burst 2 domain-specific Zscores using up to the first 10 sessions for each of the three tasks. Additional models may be considered as sensitivity analyses.

The imputation will be conducted in R using the `mice` package defaults for each variable type (e.g., predictive mean matching for the missing continuous variables (Van Buuren 2018). The number of multiple imputations will be greater than 25 (large enough to be stable, in terms of the intervention effect estimates and p-values).

Missing data approach for the secondary outcomes

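### The SAP imputes domain Z-scores in one section but lists full-burst scores only as composites in its imputation model, and leaves out Bursts 3 and 4; a cheap change would use the observed data better

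*SAP*

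**What the plan says.** SAP, Analysis of the Primary Outcome: "The domain Z-score with fewer than 18 valid sessions will be treated as missing and multiply imputed for the primary analysis". The composite is the mean of the three domain Z-scores, with Symbol Search and Grid Memory sign-reversed.

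SAP, Imputation Models for the Ambulatory Cognitive Scores, sets the same trigger at domain level for Bursts 1 and 2: "Burst measures that had fewer than 18 valid sessions for a given domain average". A Burst 2 that starts outside its window is also set to missing. The chained-equation variables then include:

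- full-burst scores: "Burst 1 composite Z-score, and Burst 2 composite Z-score";
- run-in domain data: "run-in average variables for each of the tasks 1-3 in the composite outcome";
- Burst 1 domain data: "domain-specific Zscores based on the average of the available data from up to the first 10 sessions at Burst 1";
- Burst 2 domain data: "the Burst 2 domain-specific Zscores using up to the first 10 sessions for each of the three tasks";
- arm, gender, age, education and the MOCA variables.

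The list has no full-burst domain Z-score and no Burst 3 or 4 variable. No rule says how a composite is formed when some domains are observed and others imputed. Beyond the list, the section says only: "Additional models may be considered as sensitivity analyses".

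The later data will exist. Protocol section 3: "Three additional 7-day measurement bursts will be completed at 9, 18 and 27 months post-baseline". Protocol section 8 lets a participant who withdraws temporarily rejoin.

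**The concern.** The two SAP sections can be programmed in different ways. One programmer imputes the short domain and averages it with the two observed domains. Another follows the variable list, sets the composite to missing and redraws all of it. These give different primary datasets from the same participants.

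Under the second reading, two of the three terms of the composite are known and are still replaced by draws. Sessions 11-35 of the valid Burst 2 tasks then play no part.

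Likewise, someone who misses Burst 2, or starts it outside the window, but completes month 18 or 27 has scores that should predict the missing value well. The list does not use them.

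At stake are an unambiguous primary specification and some precision in the imputed values.

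**Working it through.** **1. The plan's own figure.** Protocol section 9.2 gives 80% power for 0.35 SD with 125 per arm. With two-sided alpha 0.05 (assumed; none is stated): 0.35 × √(125/2) = 2.767; 2.767 − 1.960 = 0.807; Φ(0.807) = 79.0%. This agrees, and 277 × 0.9 = 249.3 matches the stated n = 250. The point below does not disturb this figure.

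**2. Inputs.**
- Burst-to-burst correlation about 0.90 (Protocol 9.2, from an earlier study). I apply it to each domain and to every pair of bursts; both are assumptions.
- Reliability 0.97 (Grid Memory) and 0.98 (Symbol Search) for averages over 14 days at 5 prompts a day (Protocol 2.2.3): 70 sessions, or 56 at 80% compliance.
- Visit 2 loss: 260 of 290 retained (Protocol section 3), so 30/290 = 10.3% missing before invalid or out-of-window bursts.
- Assumed: between-domain correlation 0.3; first-10 reliability 0.85 against 0.95 for a full burst.

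**3. How much the first-10 scores keep.** Spearman-Brown: session ICC = 0.97/(70 − 69 × 0.97) = 0.316. Reliability is then 0.822 for 10 sessions and 0.942 for 35. The part-whole correlation is √(0.822/0.942) = 0.93. Starting from 0.98 over 56 sessions, it is 0.96.

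**4. One domain invalid (no usable sessions), two valid.**
- Composite variance: (3 + 6 × 0.3)/9 = 0.533.
- Listed predictors (Burst 1 composite, first-10 domain scores): the multivariate-normal conditional variance of the Burst 2 composite is about 0.050.
- With the two full-burst Burst 2 domain scores and the Burst 1 domain scores: 0.19 × (1 − 2 × 0.09/1.3)/9 = 0.018, where 0.19 = 1 − 0.9².
- Reduction: 1 − 0.018/0.050 = 64%. Varying the between-burst correlation over 0.85-0.90, the between-domain correlation over 0.3-0.6 and the Color Shapes ICC over 0.15-0.32, it runs from a little over half (about 53%) to about four fifths.
- If the short task still has 10 sessions, the listed set already recovers 59-80% of the variance left after Burst 1. Adding the two full-burst scores raises this to 91-95%.

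**5. Burst 2 absent, Bursts 3 and 4 present.** On unit scale, variance given Burst 1 is 0.190. Given Bursts 1, 3 and 4 it is 1 − 3 × 0.81/2.8 = 0.132. Reduction: 1 − 0.132/0.190 = 30%. On the composite scale, 0.533 × 0.190 = 0.101 falls to 0.533 × 0.132 = 0.070. Run-in averages and MOCA are not modelled, so the gain is if anything overstated.

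**6. Effect of step 5 on the primary analysis.** With missing share m, and assumed share s of those who have later bursts, the SE gain is 1 − √[(1 − m)/(1 − m + 0.30·m·s)].

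| m | s = 0.3 | s = 0.8 |
|---|---|---|
| 10% | 0.5% | 1.3% |
| 20% | 1.1% | 2.9% |

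If all of the 10% missing had later bursts, effective N would rise from 249.3 to 249.3 + 27.7 × 0.3 = 257.6, and power from 78.9% to 80.2%. The ceiling, with nothing missing at n = 277, is 83.0%.

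**7. Effect of step 4.** The documents do not say how often exactly one domain fails, so this part cannot be sized from them.

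**The case against.** The case for leaving the text alone has several parts.

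- *The list may be predictors only.* The imputation section itself names the domain averages as the quantities treated as missing, so the two sections could be read as consistent. That makes this an ambiguity and not a proven contradiction. It still needs settling, because the composites are in the list, the full-burst domain scores are not, and no assembly rule is given.
- *Domain data are not thrown away.* A reader might infer that the model holds composites alone and discards valid domain data. The documents do not support that. Nine domain-level variables are listed (three tasks each for run-in, Burst 1 and Burst 2), and first-10 averages correlate 0.93-0.96 with 35-session averages for the two tasks with stated reliability. They also rescue information from bursts with fewer than 18 sessions. This stands.
- *The 64% is a fraction of a small remainder.* In R² terms it is a rise from about 0.91 to 0.97, and for an absent Burst 2 from about 0.81 to 0.87. This stands.
- *One domain failing alone is probably uncommon.* Protocol section 3 has the tasks follow the same surveys, so a participant short on one will usually be short on all. This is plausible, although the SAP allows session counts to differ by domain.
- *Other imputation models are allowed.* They are optional and only for sensitivity, so they do not define the primary analysis.

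A reader might also infer that the domain results will fail to add up to the composite because of this list. That does not follow. The SAP assigns secondary outcomes, which include the individual tasks, to adjusted complete-case analysis, and the supportive Burst 2 analysis uses each task's own score in separate models. Sharing imputed sets would only align the participants.

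**Conclusion.** The point holds as a specification gap with a better method available at little cost. The SAP should say whether full-burst domains or the composite are imputed. As listed, the model redraws composites that are two-thirds observed and ignores Bursts 3 and 4.

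The gain is modest: about 0.5-1.3% of the primary standard error at 10% missing and 1-3% at 20% from the later bursts, or at most about 1.3 power points at 10% missing. There is no gain from those bursts for permanent dropouts before month 9. The domain-level gain is large for each affected participant, but the number affected is unknown.

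These sizes rest on exchangeable burst correlations near 0.9, assumed between-domain correlations and Color Shapes reliability, and an assumed 30-80% of missing participants with later bursts. A reader might infer that the current plan is biased or that its missing-at-random assumption fails. Neither is shown.

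**What to change.** In SAP, Imputation Models for the Ambulatory Cognitive Scores:

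1. Impute the three full-burst domain Z-scores at Bursts 1 and 2 whenever the 18-session or window rule makes them missing.
2. Derive each composite passively from observed plus imputed domains, so that valid observed domains are kept. Do not let a composite predict its own components.
3. Keep the run-in and first-10 scores, arm, stratification variables and MOCA terms as predictors.
4. Add Burst 3 and 4 scores and any out-of-window Burst 2 scores as auxiliary variables. State whether first-10 scores from an out-of-window Burst 2 may be used.
5. Allow the same imputed sets to serve the supportive Burst 2 analysis of each domain.

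Align the sentence in Analysis of the Primary Outcome with this.

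The cost is SAP wording and a few more variables in the mice call, with no new data. The downside is a slightly larger model with strongly correlated predictors, some with missing values of their own, so convergence and stability should be checked.
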